## NON-INTERVENTIONAL (NI) STUDY PROTOCOL

#### **Study information**

Title	Investigating the effect of the 13-valent pneumococcal conjugate vaccine	
1 itie	on major adverse cardiovascular events among Medicare enrollees aged	
	$\geq$ 65 years in the United States	
Protocol number	B1851222	
Protocol version identifier	1.0	
Date	28 March 2025	
EU Post Authorization Study (PAS) register number	EUPAS1000000520	
Active substance	World Health Organization's Anatomical Therapeutic Chemical (ATC) code - J07AL02	
	13-valent pneumococcal conjugate vaccine	
Medicinal product	Prevenar 13	
Research question and objectives	Research question:	
	Is prior receipt of PCV13 associated with reduced risk of major adverse cardiovascular events (MACE) outcomes in adults aged $\geq$ 65 years?	
	The primary objective of this study is to:	
	
 
Evaluate the effect of the 13-valent pneumococcal conjugate vaccine (PCV13) receipt on the risk of major adverse cardiovascular events (MACE) at 1 and 3 years of follow-up among adults aged ≥65 years
 
	
	The secondary objectives of this study are to:	
	
 
Evaluate the effect of PCV13 receipt on the risk of myocardial infarction at 1 and 3 years of follow-up among adults aged ≥65 years
 
	
	
 
Evaluate the effect of PCV13 receipt on the risk of stroke at 1 and 3 years of follow-up among adults aged ≥65 years
 
	

PFIZER CONFIDENTIAL

CT24-WI-GL02-RF02 6.0 Non-Interventional Study Protocol Template For Secondary Data Collection Study Page 1 of 53

	
 
3. Evaluate the effect of PCV13 receipt on the risk of hospitalization due to heart failure at 1 and 3 years of follow-up among adults aged ≥65 years
 
4. Examine the degree to which community-acquired pneumonia (CAP) mediates the relationship between PCV13 receipt and MACE at 1 year of follow-up among adults aged >=65 years
 
	
Country(ies) of study	United States	
Author	[name] Pfizer Inc. [name] United States [contact]	
in writing, by accepting	confidential information belonging to Pfizer. Except as otherwise agreed to or reviewing this document, you agree to hold this information in confidence	

# 2. LIST OF ABBREVIATIONS

Abbreviation	Definition		
AE	Adverse event		
ACIP	Advisory Committee on Immunization Practices		
ATC	Anatomical Therapeutic Chemical		
CAD	Coronary artery disease		
САР	Community-acquired pneumonia		
CCW	Chronic Conditions Warehouse		
CDC	Centers for Disease Control and Prevention		
CDE	Controlled Direct Effect		
CI	Confidence intervals		
CIF	Cumulative incidence function		
CFR	Code of Federal Regulations		
CMS	Centers for Medicare and Medicaid Services		
COPD	Chronic obstructive pulmonary disease		
СРТ	Current Procedural Terminology		
DUA	Data Use Agreement		
EC	Ethics Committee		
ENCePP	European Network of Centres for Pharmacoepidemiology and Pharmacovigilance		
EPIC	Etiology of Pneumonia in the Community		
FDA	Food and Drug Administration		
FFS	Fee-for-Service		
GPP	Guidelines for Good Pharmacoepidemiologic Practice		
HCPCS	Healthcare Common Procedure Coding System		

PFIZER CONFIDENTIAL

CT24-WI-GL02-RF02 6.0 Non-Interventional Study Protocol Template For Secondary Data Collection Study Page 5 of 53

НІРАА	Health Insurance Portability and Accountability Act
HR	Hazard ratio
ICD-9-CM	International Classification of Diseases, Ninth Revision, Clinical Modification
ICD-10-CM	International Classification of Diseases, Tenth revision, Clinical Modification
ICD-9-PCS	International Classification of Diseases, Ninth Revision, Procedure Coding System
ICD-10-PCS	International Classification of Diseases, Tenth Revision, Procedure Coding System
IPCW	Inverse probability of censoring weighting
IPTW	Inverse probability of treatment weighting
IRB	Institutional Review Board
ISPOR	International Society for Pharmacoeconomics and Outcomes Research
LTCF	Long-term care facility
MACE	Major adverse cardiovascular events
MI	Myocardial infarction
MMWR	Morbidity and Mortality Weekly Report
NDC	National drug code
NIE	Natural Indirect Effect
PAD	Peripheral arterial disease
PASS	Post-authorization safety study
PCV	Pneumococcal conjugate vaccine
PCV13	13-valent pneumococcal conjugate vaccine
PPSV23	23-valent pneumococcal polysaccharide vaccine
PS	Propensity score

CT24-WI-GL02-RF02 6.0 Non-Interventional Study Protocol Template For Secondary Data Collection Study Page 6 of 53

SAP	Statistical analysis plan
SAS	Statistical Analysis System
SD	Standard deviation
SMD	Standardized mean difference
SNF	Skilled nursing facility
SQL	Structured Query Language
STEMI	ST elevation myocardial infarction
ssUAD	Serotype-specific urinary antigen detection
TIA	Transient ischemic attacks
US	United States
VRDC	Virtual Research Data Center

PFIZER CONFIDENTIAL CT24-WI-GL02-RF02 6.0 Non-Interventional Study Protocol Template For Secondary Data Collection Study Page 7 of 53

# 4. ABSTRACT

Title	Investigating the effect of the 13-valent pneumococcal conjugate vaccine on major adverse cardiovascular events among Medicare enrollees aged ≥65 years in the United States	
	Version 1.0	
	Protocol date: 28 March 2025	
	Author: [name]	
	Affiliation: Pfizer Inc., [name], United States	
Rationale and background	Adult patients with community-acquired pneumonia (CAP), particularly pneumococcal CAP, are at substantial risk of major cardiovascular events (MACE). There is evidence from observational studies that respiratory vaccines, influenza vaccination in particular, can reduce the risk of MACE in adults.  However, data on the potential effects of 13-valent pneumococcal conjugate vaccine (PCV13) to reduce MACE in adults are limited.	
Research	Research question:	
question and objectives	Is prior receipt of PCV13 associated with reduced risk of major adverse cardiovascular events (MACE) outcomes in adults aged $\geq$ 65 years?	
	The primary objective of this study is to:	
	
 
Evaluate the effect of PCV13 receipt on the risk of major adverse cardiovascular events (MACE) at 1 and 3 years of follow-up among adults aged ≥65 years
 
	
	The secondary objectives of this study are to:	
	
 
Evaluate the effect of PCV13 receipt on the risk of myocardial infarction at 1 and 3 years of follow-up among adults aged ≥65 years
 
	
	
 
Evaluate the effect of PCV13 receipt on the risk of stroke at 1 and 3 years of follow-up among adults aged ≥65 years
 
	
	
 
Evaluate the effect of PCV13 receipt on the risk of hospitalization due to heart failure at 1 and 3 years of follow-up among adults aged ≥65 years
 
	
	
 
Examine the degree to which CAP mediates the relationship between PCV13 receipt and MACE at 1 year of follow-up among adults aged >=65 years
 
	
Study Design	The study will be a retrospective cohort study using Medicare administrative claims data.	

PFIZER CONFIDENTIAL

CT24-WI-GL02-RF02 6.0 Non-Interventional Study Protocol Template For Secondary Data Collection Study Page 9 of 53

	The index date for the vaccinated cohort is defined as the first date of PCV13 vaccination. For the unvaccinated cohort, the index date is defined as the date of the first available healthcare claim that occurs after the eligibility date (September 14, 2014) and ensures a six-month continuous period following enrollment.
Population	The study cohort will be identified using administrative claims. The study population includes individuals aged $\geq$ 65 years of age and enrolled in Medicare Fee-for-Service (FFS) Parts A and B as of September 14, 2014. Individuals are required to have at least 6 months of prior continuous enrollment in Medicare FFS Parts A and B as of the index date to be included in the study. Individuals with evidence of PCV13 receipt prior to index, evidence of PPSV23 receipt in the 365 days prior to index, enrollment in Medicare Part C between September 14, 2014 and index, a high-risk condition for CAP in the 365d prior to index, iatrogenic immunosuppression in the 6 months prior to index, a pneumonia diagnosis code in the hospital setting in the 365d prior to index, or a MACE event in the hospital, skilled nursing facility (SNF), or long-term care facility (LTCF) setting in the 365d prior to index will be excluded. PCV13 vaccinated time segments are excluded if the individual had a pneumonia diagnosis code in the hospital setting or a MACE diagnosis code in the hospital, SNF, or LTCF setting in the 13 days after PCV13 vaccination. For PCV13 vaccinated individuals contributing unvaccinated and vaccinated time segments, inclusion/exclusion criteria and baseline characteristics will be assessed separately for each index date.
Variables	Exposure : PCV13 vaccination
	Outcomes : Any MACE, Myocardial infarction, Stroke, Stroke sensitivity, Heart Failure, Cataract surgery (Negative control outcome), lipoma (Negative control outcome), Follow-up time (descriptive)
	Covariates: Age, Sex, Race/ethnicity, Geographic region, Respiratory season of index, Year of index date, Month of index date, Outpatient heart failure, Coronary artery disease (CAD), Hypertension, Valvular heart disease, Unstable angina, Stable angina, Aortic aneurysm and dissection, Arrhythmia, Atrial fibrillation, Cardiomyopathy, Peripheral arterial disease (PAD), Pulmonary hypertension, Rheumatic heart disease, Congenital heart defects, High cholesterol, High triglycerides, Metabolic syndrome, Autoimmune disease, Transient ischemic attacks (TIA), Dementia, Chronic obstructive pulmonary disease (COPD), Connective tissue disease, Peptic ulcer disease, Chronic liver disease, Diabetes mellitus, Hemiplegia, Solid tumor, Chronic lung disease, Asthma, Alcoholism, Smoking, Obesity, Functional/mobility status, Physical/wellness visit, Number of hospitalizations in the prior 180d, Number of outpatient visits in the prior 180d, Nursing home stay, Skilled nursing facility (SNF) stay, Influenza vaccine, Type of index influenza vaccine administered, PPSV23 receipt, Respiratory failure, Influenza infection, Outpatient pneumonia, Telehealth visits, Flu test in the prior 365 days, Number of labs ordered in the prior 365 days, Number of lipid lab tests ordered in the prior 365 days, Echocardiogram, Electrocardiogram

CT24-WI-GL02-RF02 6.0 Non-Interventional Study Protocol Template For Secondary Data Collection Study Page 10 of 53

Data source	The Medicare administrative claims database includes individuals $\geq$ 65 years of age and individuals with a qualifying disability who are enrolled in a Medicare fee-for- service plan. The database includes enrollment information for these individuals as well as adjudicated claims for inpatient care, ambulatory care, and outpatient prescriptions.
Study size	Treatment-to-control group allocation ratio (2:3) and the hazard rate for the control group (0.0507) were estimated based on a feasibility analysis using the Medicare fee-for-service claims database. We assumed a hazard ratio of 0.85 for the PCV13 vaccinated compared to the unvaccinated group and used a two-sided test with a significance level of 5%. To account for different follow-up durations, we calculated required sample sizes for average follow-up durations of 0.75, 1, 2.75, and 3 years. The sample sizes were calculated to achieve 80% power in each scenario.
	Assuming an average follow-up duration of 3 years, the study will require a minimum sample size of 9,600 adults. Assuming an average follow-up duration of 0.75 years, the study will require a minimum sample size of 36,485 adults.
	A feasibility analysis using the Medicare fee-for-service claims database estimated approximately 25 million adults are eligible for inclusion in the study during the years of interest.
Data analysis	Separate analyses will be conducted with 0 to 1 year and 0 to 3 years of follow-up. A cause-specific Cox proportional hazards model with time-varying covariates will be used for the primary analysis. The cause-specific cox model will be used to estimate hazard ratios (HRs) for each MACE outcome, comparing PCV13 vaccinated with PCV13 unvaccinated Medicare enrollees. The weighted cumulative incidence function (CIF) will also be presented, describing and accounting for competing risk events. The analysis will utilize Inverse Probability of Treatment Weighting (IPTW) to adjust for baseline differences between the vaccinated and unvaccinated cohorts. Covariates with residual imbalance after weighting will be included in the final models for further adjustment to control for potential confounders. The primary analysis models will also adjust for influenza vaccination status during follow-up as a time-varying covariate.
	The study will also include a mediation analysis, which is considered a secondary analysis. The mediation analysis will estimate the direct and indirect effects of PCV13 receipt on MACE, examining the extent to which the relationship between PCV13 and MACE within 1 year of follow-up is mediated by CAP. The mediation analysis will utilize the product method,  which uses a logistic weighted mediation model to assess the mediator and a Cox model weighted outcome model to derive the HR and confidence intervals (CI).
	The study will also include three sensitivity analyses. The first sensitivity analysis will incorporate the Fine-Gray model, which provides an alternative to the cause-specific Cox model and helps ensure the robustness of the findings when comparing different analytical approaches to competing risks. Second, the study will include a sensitivity analysis using an alternative definition of stroke. The primary analysis

CT24-WI-GL02-RF02 6.0 Non-Interventional Study Protocol Template For Secondary Data Collection Study Page 11 of 53

	will include ischemic stroke only and the sensitivity analysis will include hemorrhagic and ischemic stroke. The third sensitivity analysis will modify the definition of CAP in the mediation analysis to only include CAP cases in the hospital setting.				
Milestones	Completion of feasibility assessment : 24 July 2024				
	Registration, HMA-EMA Catalogues of RWD studies: 11 April 2025				
	Expected Start of data collection : 15 April 2025				
	Expected End of data collection : 01 September 2025				
	Expected Final study report : 01 April 2026				

# **5. AMENDMENTS AND UPDATES**

None.

PFIZER CONFIDENTIAL CT24-WI-GL02-RF02 6.0 Non-Interventional Study Protocol Template For Secondary Data Collection Study Page 13 of 53

#### 6. MILESTONES

Milestone	Planned Date
Completion of feasibility assessment	24 July 2024
Registration in the HMA-EMA Catalogues of RWD studies	11 April 2025
Start of data collection	15 April 2025
End of data collection	01 September 2025
Final study report	01 April 2026

### 7. RATIONALE AND BACKGROUND

Community-acquired pneumonia (CAP) is a major cause of morbidity and mortality in older adults. A systematic review conducted in 2020 reported that in the United States (US), the estimated annual incidence of hospitalized CAP among adults aged  $\geq 65$  years ranges from 847 to 3500 per 100,000 persons. In a prospective study of adults hospitalized with CAP conducted in Louisville, Kentucky during 2014 to 2016, 6.5% of patients died during hospitalization, and mortality increased to 30.6% at 1 year after hospitalization. CAP can be caused by a wide range of viral, bacterial, and fungal pathogens, with Streptococcus pneumoniae typically reported as a leading bacterial cause. In the Etiology of Pneumonia in the Community (EPIC) study conducted by the US Centers for Disease Control and Prevention (CDC) at 5 hospitals during 2010-2012, S. pneumoniae was the most common bacteria identified and the third most common pathogen overall, behind rhinovirus and influenza virus. A systematic literature review published in 2020 that included 146 studies evaluating CAP etiology in adults in developed countries found that S. pneumoniae remains the most common bacterial cause of CAP, despite some declines in incidence in recent years. Detection of pneumococcal CAP is underestimated using traditional diagnostic methods such as sputum culture, as evidenced by the EPIC study, which found that use of serotype-specific urinary antigen detection (ssUAD) assay that detects the serotypes included in the 13-valent pneumococcal conjugate vaccine (PCV13) substantially increased detection of pneumococcal pneumonia. The Louisville, Kentucky adult CAP study conducted ssUAD testing for 24 pneumococcal serotypes and found that 13% of patients had pneumococcal pneumonia. They estimated that each year in the United States, more than 225,000 adults are hospitalized for pneumococcal CAP, and one quarter of these patients die within one year after hospitalization.

Cardiovascular complications are common during and after CAP, with up to 30% of hospitalized CAP patients experiencing a major adverse cardiovascular event (MACE). Cardiovascular complications during and after CAP are closely associated with poor outcomes including mortality. Several pathophysiological mechanisms may contribute to the association between CAP and MACE outcomes, such as systemic inflammation resulting from pneumonia, or disruption of a previously stable plaque leading to an acute myocardial infarction. Additionally, there is evidence that the pathogens causing pneumonia, including *S. pneumoniae* in particular, can directly damage the cardiovascular system. Adult patients with pneumococcal CAP are at substantial risk for MACE. MACE outcomes are also common in adults with invasive pneumococcal disease. In a cohort of Dutch adults aged  $\geq$ 45 years, 4.2% experienced a cardiovascular event within one year after hospitalization for invasive pneumococcal disease, with acute coronary syndromes primarily occurring within 12 days of admission. Evidence from in vitro and animal studies has implicated the pneumococcal toxin pneumolysin in cardiac injury. In a non-human primate model of severe

PFIZER CONFIDENTIAL

CT24-WI-GL02-RF02 6.0 Non-Interventional Study Protocol Template For Secondary Data Collection Study Page 14 of 53 pneumococcal pneumonia, examination of cardiac tissue showed that *S. pneumoniae* invaded the myocardium and induced cardiac injury with necroptosis and apoptosis, and cardiac scarring occurred after antibiotic treatment. Studies in mouse models have determined that heart damage varies by pneumococcal strain. Similarly, clinical studies have revealed that MACE in patients with invasive pneumococcal disease are serotype dependent.

The 13-valent pneumococcal conjugate vaccine (PCV13) provides protection against invasive pneumococcal disease and vaccine-type pneumococcal CAP in older adults. Additionally, PCV13 is associated with reduced incidence of all-cause CAP and lower respiratory infections in older adults. There is evidence that respiratory vaccines, influenza vaccination in particular, can reduce the risk of MACE in adults. Several observational studies have investigated whether the 23-valent pneumococcal polysaccharide vaccine (PPV23) provides protection against MACE outcomes such as myocardial infarction and stroke, with results varying by study and outcome. To date, no published data on the effectiveness of PCV13 on MACE outcomes are available, however a retrospective cohort study in Hong Kong adults aged  $\geq$ 65 investigated whether sequential vaccination with PCV13 and 23-valent pneumococcal polysaccharide vaccine (PPSV23) would provide protection against cardiovascular diseases compared with a single pneumococcal vaccine. Tong et al. found that older adults who received sequential dual vaccination had a lower risk of cardiovascular diseases [Hazard Ratio (95% confidence interval): 0.75 (0.71, 0.80)] compared with those who received a single pneumococcal vaccine. Post-hoc analysis indicated that the decreased cardiovascular disease risk was mediated by a reduction in all-cause pneumonia.

This observational study was designed to evaluate the effect of PCV13 on MACE outcomes among adults aged  $\geq 65$  years in the United States using a large claims database from the Medicare health insurance program.

The biological mechanism behind the potential impact of PCV13 receipt on risk of MACE is through a reduction in all-cause pneumonia, which is an infection commonly associated with cardiovascular complications. While the intention of the study is to investigate the hypothesis that PCV13 receipt reduces the risk of certain adverse events (e.g. MACE, myocardial infarction (MI), stroke, etc) through the prevention of pneumonia, it is possible that during this enquiry, the study may collect data which indicates an unanticipated safety signal.

This noninterventional study is designated as a post-authorization safety study (PASS) and is conducted voluntarily by Pfizer.

# 8. RESEARCH QUESTION AND OBJECTIVES

Research question:

Is prior receipt of PCV13 associated with reduced risk of major adverse cardiovascular events (MACE) outcomes in adults aged  $\geq 65$  years?

The primary objective of this study is to:

1. Evaluate the effect of PCV13 receipt on the risk of major adverse cardiovascular events (MACE) at 1 and 3 years of follow-up among adults aged ≥65 years

The secondary objectives of this study are to:

PFIZER CONFIDENTIAL CT24-WI-GL02-RF02 6.0 Non-Interventional Study Protocol Template For Secondary Data Collection Study Page 15 of 53

- 1. Evaluate the effect of PCV13 receipt on the risk of myocardial infarction at 1 and 3 years of follow-up among adults aged ≥65 years
- 2. Evaluate the effect of PCV13 receipt on the risk of stroke at 1 and 3 years of follow-up among adults aged ≥65 years
- 3. Evaluate the effect of PCV13 receipt on the risk of hospitalization due to heart failure at 1 and 3 years of follow-up among adults aged ≥65 years
- 4. Examine the degree to which CAP mediates the relationship between PCV13 receipt and MACE at 1 year of follow-up among adults aged >=65 years

### 9. RESEARCH METHODS

#### 9.1. Study Design

This structured secondary data collection study will be a retrospective cohort study using Centers for Medicare and Medicaid Services (CMS) Medicare data to examine the effect of PCV13 receipt on the risk of MACE among adults aged  $\geq 65$  years in the United States. Individuals will be identified using Medicare Fee-for-Service (FFS) Parts A and B enrollment and claims data.

The analysis will be conducted at the time-segment level using a target trial emulation approach. In this time-segment design, individuals who receive a PCV13 vaccine during the study period can contribute up to two time segments during the follow-up period: a PCV13 unvaccinated time segment and a PCV13 vaccinated time segment. Each segment will be attributed to the appropriate vaccination exposure status cohort, resulting in the individual having two separate index dates included in the analysis. Inclusion/exclusion criteria and baseline characteristics will be assessed separately for these two index dates. For PCV13 unvaccinated patients, multiple eligible times may be identified within the study period, but only the first eligible time will be selected due to the large sample size of the unvaccinated cohort. Individuals who remain unvaccinated throughout the entire follow-up period can contribute a maximum of 1 time segment, which will be attributed to the unvaccinated cohort. All analyses will be conducted based on time-segment level data, which allows the exposure variable – PCV13 vaccination – to be treated as time-invariant within each segment.

The index date for the vaccinated cohort is defined as the date of first PCV13 vaccination. For the unvaccinated cohort, the index date is defined as the date of the first available healthcare claim that occurs after the eligibility date (September 14, 2014) and ensures a six-month period of continuous enrollment prior to the index date. Eligible vaccinated and unvaccinated index dates are 1) between September 14, 2014 and November 30, 2019 and 2) after the individual has at least 6 months of continuous enrollment in Medicare FFS Parts A and B. The 6 months of continuous enrollment prior to the index date for each time segment will be used as the baseline period. Baseline covariates, including demographics, preventative care behaviors, and comorbidities will be assessed during this period.

During PCV13 unvaccinated time segments, unvaccinated individuals will be followed from their unvaccinated index date until experiencing one of the following: 1) the outcome, 2) disenrollment, 3) death, 4) receipt of a PCV13 vaccine, 5) receipt of a PPSV23 vaccine, or 6) the end of the study period. During PCV13 vaccinated time segments, vaccinated individuals will be followed starting 14 days after their first PCV13 vaccination and until experiencing one of the following: 1) the outcome,

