# 9.2.1. Inclusion Criteria

Patients must meet all of the following inclusion criteria as of the index date to have the respective time segment included in the study:

- 1. Enrolled in Medicare FFS Parts A and B as of September 14, 2014 (date of PCV13 ≥65 recommendation in the Morbidity and Mortality Weekly Report (MMWR))
- 2. Aged ≥65 years as of September 14, 2014
- 3. Continuous enrollment in Medicare FFS Parts A and B for at least 6 months prior to the index date

[figure not shown]

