### 9.3.5. Covariates

#### Table 5.Covariates

Variable	Role	Operational definition	Measurement period
Age	Patient characteristics	
 
The number of years between the index date and the patient birth year for each time segment. Age will be reported overall and in the following categories: 65-69 years, 70-74 years, 75-79 years, 80-84 years, and 85+ years.
 
Continuous statistics including mean, standard deviation (SD), median (Q1-Q3), minimum, and maximum, will also be summarized.
 
	Baseline
Sex	Patient characteristics	Sex will be reported as Male (1), Female (2), and Unknown (0)	Baseline
Race/ethnicity	Patient characteristics	Self-reported race will be reported as White (1), Black (2), Other (3), Asian (4), Hispanic (5), North American Native (6), and Unknown (0).	Baseline
Geographic region	Patient characteristics	
 
US geographic region will be derived from the patient state and categorized into the following:
 
Northeast – Connecticut, Maine, Massachusetts, New Hampshire, Rhode Island, Vermont, New Jersey, New York, Pennsylvania
 
Midwest – Indiana, Illinois, Michigan, Ohio, Wisconsin, Iowa, Kansas, Minnesota, Missouri, Nebraska, North Dakota, South Dakota
 
South – Delaware, District of Columbia, Florida, Georgia, Maryland, North Carolina, South Carolina, Virginia, West Virginia, Alabama, Kentucky, Mississippi, Tennessee, Arkansas, Louisiana, Oklahoma, Texas
 
	Baseline

PFIZER CONFIDENTIAL

CT24-WI-GL02-RF02 6.0 Non-Interventional Study Protocol Template For Secondary Data Collection Study Page 27 of 53

		
 
West – Arizona, Colorado, Idaho, New Mexico, Montana, Utah, Nevada, Wyoming, Alaska, California, Hawaii, Oregon, Washington
 
Other/unknown – Puerto Rico/ unknown region
 
	
Respiratory season of index	Patient characteristics	The respiratory season of the individual's index date for each time segment.August 2014 – July 2015 August 2015 – July 2016 August 2016 – July 2017 August 2017 – July 2018 August 2018 – July 2019 August 2019 – November 2019	Baseline
Year of index date	Patient characteristics	The year of the individual's index date for each time segment. 2014, 2015, 2016, 2017, 2018, 2019.	Baseline
Month of index date	Patient characteristics	The month of the individual's index date for each time segment. January, February, March, April, May, June, July, August, September, October, November, or December.	Baseline

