# **Balancing and Covariate Adjustment Methods**

The analysis will utilize inverse probability of treatment weighting (IPTW) to adjust for differences in the baseline characteristics between the PCV13 vaccinated and PCV13 unvaccinated cohorts. IPTW creates a pseudo-population in which the distribution of measured baseline covariates is independent of treatment assignment, thereby mimicking randomization.

Propensity scores (PS) will be created using a logistic regression model and used to calculate the inverse probability of treatment weights. Standardized mean differences (SMD) will be used to assess covariate balance before and after weighting. An absolute standardized difference less than or equal to

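### Taking only the first eligible claim concentrates unvaccinated index dates in late 2014–2015 and risks leaving later vaccinated index years with almost no unvaccinated starts to compare

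*Protocol*

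**What the plan says.** The cohort is closed. Section 9.2.1 requires each person to be "Enrolled in Medicare FFS Parts A and B as of September 14, 2014" and "Aged ≥65 years as of September 14, 2014".

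Section 9.1 sets different index rules for the two cohorts. For the unvaccinated, "the index date is defined as the date of the first available healthcare claim that occurs after the eligibility date (September 14, 2014", subject to six months of prior enrollment. Later eligible times are acknowledged but not used: "only the first eligible time will be selected due to the large sample size of the unvaccinated cohort". For the vaccinated: "The index date for the vaccinated cohort is defined as the date of first PCV13 vaccination". The window is common to both: "Eligible vaccinated and unvaccinated index dates are 1) between September 14, 2014 and November 30, 2019".

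Table 5 lists season, month and year of index as baseline covariates, the last as "The year of the individual's index date for each time segment". Section 9.7 relies on weighting for comparability: "IPTW creates a pseudo-population in which the distribution of measured baseline covariates is independent of treatment assignment". It specifies stabilized weights, makes truncation optional, sends residual imbalance to the Cox model and leaves the final propensity covariates to the SAP. The protocol reports no distribution of index dates and specifies no overlap check by index date.

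**The concern.** A person enrolled on 14 September 2014 usually meets the unvaccinated rule at the next claim. A vaccinated person's index date is whenever the vaccine was given, up to five years later. Index calendar time is therefore tied to exposure by the design, and either handling in the propensity model has a cost.

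- With year, month and season in the model, later years may hold almost no unvaccinated starts. Weights there become extreme or undefined, and Cox adjustment extrapolates.
- With them left out, exposure is confounded with secular change in MACE rates and with outcome coding. Appendix Table 2 restricts ICD-9-CM infarction codes to the initial episode of care, while its ICD-10-CM list adds type 2 and subsequent infarction.

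The primary MACE hazard ratio is at stake, and sample size gives no protection. Section 9.5 implies an average hazard of 0.4 × 0.85 × 0.0507 + 0.6 × 0.0507 = 0.0477 a year. If all of the roughly 25 million eligible people were followed for one year, that gives about 1.19 million events and an unweighted SE of the log hazard ratio of 1/√(1.19 million × 0.24) ≈ 0.002. Even a small systematic error would look decisive.

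**Working it through.** **The plan's own figure.** The only recomputable figure is the sample size. Freedman's formula with 2:3 allocation and HR 0.85 needs 1,284 events. The one-year event probability is 0.4(1 − e^(−0.85 × 0.0507)) + 0.6(1 − e^(−0.0507)) = 0.0465, so N ≈ 27,600 against the stated 27,520. The stated sample sizes reproduce within 1% and are not disputed. There is no stated index-date distribution to reproduce.

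**Inputs from the protocol.** The index window is 14 September 2014 to 30 November 2019, or 1,903 days. The part up to 31 December 2015 is 473 days, and 473/1,903 = 25%. The vaccinated share is 39.6%, taken as 40:60.

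**Assumptions, not in the protocol.**
- 1, 2, 4 or 8 claim-days per person-year.
- 5% waiting up to six months for the enrollment requirement.
- 0 to 30% delayed up to one year by a look-back exclusion.
- 25% (uniform uptake), 48% or 65% (front-loaded) of vaccinated index dates by end-2015.

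**Step 1: share of unvaccinated starts by end-2015.** With claim rate r and no delay, the share is 1 − e^(−1.298r), where 1.298 years runs to 1 January 2016. This gives 0.727, 0.925, 0.994 and above 0.999 for r = 1, 2, 4 and 8. Adding the delays gives the ranges in the table.

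**Step 2: propensity from index year alone.** PS(y) = 0.4v(y) / [0.4v(y) + 0.6u(y)], where v(y) and u(y) are the shares of vaccinated and unvaccinated index dates in year y. For 2017, with uniform uptake, r = 2 and no delay:
- v = 365/1,903 = 0.192
- u = e^(−2 × 2.300) − e^(−2 × 3.299) = 0.0087
- PS = 0.0768 / (0.0768 + 0.0052) = 0.94 (0.93 with the enrollment wait)

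**Results across all delay and uptake scenarios.** Overlap is the sum over index years of the smaller of the two shares (0 = none, 1 = full).

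| Claim-days per year | Unvaccinated index by end-2015 | Overlap of index years | PS for 2017 |
|---|---|---|---|
| 1 | 67–73% | 0.52–0.92 | 0.43–0.67 |
| 2 | 87–92% | 0.33–0.78 | 0.80–0.93 |
| 4 | 97–99% | 0.25–0.64 | at least 0.99 |
| 8 | over 99% | 0.18–0.48 | above 0.99 |

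**Step 3: consequence for the weights.** The stabilized weight for an unvaccinated segment is 0.6/(1 − PS). At 2 claim-days a year, the largest untruncated weight is 49 to 416, and the unvaccinated effective sample size is 3% to 53% of nominal. At 4 or more, the latest years contain essentially no unvaccinated starts, and the weights are undefined. For 2014–2015 the propensity stays between about 0.04 and 0.73, so common support exists there.

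**The case against.** The strongest reply has four parts.

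- **Overlap.** Yearly PCV13 uptake is not given, and overlap ranges from 0.18 to 0.92. A reader might infer that the cohorts barely overlap. The protocol does not support that: vaccinations in 2014–2015 have unvaccinated counterparts, and look-back exclusions push some first eligible times later. This stands.
- **Person-time.** Unvaccinated segments can run 1,095 days (Table 4), so person-time reaches 2017–2018. This stands only in part. If the Cox time scale is time since index, as the 1- and 3-year limits suggest, a 2014 start at day 10 is still set against a 2018 start at day 10.
- **Weighting.** A reader might infer that IPTW cannot repair the imbalance at all. That is too strong, because Table 5 offers the calendar covariates and weighting can work where support exists. Age is also taken at each index date, so ageing need not be confounded. But no choice of covariates in the SAP creates unvaccinated starts in years that have almost none.
- **Bias.** A reader might infer a specific spurious benefit. Simulations with no true effect gave hazard ratios of 0.93–0.99, but only under an assumed 2.5-fold hazard after older MACE and a reading in which excluded people enter once their look-back bar lapses. Without that hazard the result was 0.99 (SE 0.009) at one year and 1.00 at three. If people failing the exclusions on the date of their earliest healthcare visit billed after 14 September 2014 are simply dropped, it was 1.03. Neither size nor direction is established.

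Nor can the bias be called as large as the vaccine signal. Such a bound, 0.035 × 0.30/0.0507 × 0.13 = 2.7% of MACE, counts only pneumococcal hospital CAP. Section 7 names all-cause pneumonia as the pathway, and Table 3 counts CAP in any setting.

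**Conclusion.** The concern holds as a structural fault in the index rule. Under every claim rate tried, at least two thirds of unvaccinated index dates fall in the first quarter of the window, while vaccinated dates may run to its end. Near non-positivity for 2017 onward follows at 2 or more claim-days a year. At 1 claim-day a year the imbalance is milder and weighting could largely cope. The severity therefore rests on claim frequency and yearly uptake, neither of which the protocol reports. The effect on the hazard ratio remains undetermined. The only reason given for the rule is sample size, yet about 25 million eligible people against a largest stated requirement of 36,485 leaves ample room to spread index dates. The protocol fixes the rule, so it should be changed before the primary analysis.

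**What to change.** Replace the first-eligible-time rule in section 9.1 with unvaccinated index dates aligned to vaccination dates, by one of two routes:

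1. Sequential monthly trials. In each calendar month, compare people vaccinated that month with people who are eligible and not yet vaccinated.
2. One sampled eligible claim date per unvaccinated person, drawn so that the index-month distribution matches the vaccinated cohort. Sample from people not yet vaccinated on that date, whether or not they are vaccinated later.

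In either case, estimate the propensity score within, or conditional on, index month or quarter. Tabulate index dates by cohort and report overlap and weights by index period. At minimum, keep the present rule but restrict the primary comparison to index periods with common support, and state that the estimate applies to those periods.

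The cost is a protocol amendment, matching SAP text and more programming. Person-level robust variance is needed if people enter several trials. Later unvaccinated starts have shorter follow-up, because the study ends on 31 December 2019 and the full 1,095 days is possible only for index dates up to the end of 2016. The same limit already applies to late vaccinated starts. No new data are needed.
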